**REVISION HISTORY**

Revision #	Version Date	Summary of Changes	Consent Change?
2	19AUG2020	Addition of AE/SAE Language	No
3	23SEP2020	Removing “vitals” from Summary of Events Table, this was an error	Yes
4	12NOV2020	Addition of Endocrine Clinic Intake Room and Outpatient Lab for Study Visits added. Addition of IRB approved recruitment flyers and Scope ad. Added recruitment at the Down Syndrome Clinic and associated Down Syndrome Support Group.	Yes
5	29MAR2021	Updated Sections 2.2, 11.0, and 12.0 to increase maximum age from less than 5 to less than 10 years. Updated Section 15.0 to increase study compensation to \$50.00 per visit for a total of \$150.00 for completion of all study visits. Corrected formatting in Section 28.00. Changed “Consent” to “Consent/Accent” in Summary of Events Table.	Yes
6	17JUN2021	Updated TOC to reflect correct page numbers, removed repetitive screening language, clarified that SOC visit labs must typically be within 6 weeks of baseline visit, clarified that head circumference should be obtained for	Yes

		participants less than 2 years old, added that drug can be shipped or given to participants at CMH location, Recruitment at DS clinic described more clearly, changed protocol version and date. Updated Schedule of Events to reflect correct study visit days.	
7	29OCT2021	Reformatted protocol to match latest CM Research IRB version, and updated TOC to reflect changes; replaced Summary of Events table with Table of Events; redefined study drug vs control, inclusion/exclusion criteria, & identification/pre-screening/recruitment of participants; more clearly explained and defined study procedures, including blood collection, & study surveys; added clarification to consent/assent process and assessment of participant's ability to assent; updated withdrawal of participants language to allow study staff to withdraw due to study conduct concerns; clarified AE/SAE monitoring and investigator's responsibilities; clarified statistical analysis, data and specimen management, and study setting/location; various changes in grammar and word usage to make language and content consistent throughout the protocol	Yes
8	12NOV2021	Typo in exclusion criteria: $\geq$ changed to $\leq$	No
9	13JAN2022	PQL survey moved in Schedule of Events table in protocol and ICF	Yes
10	22MAR2022	Remove PQL survey from visit 3 schedule of events. Reworked primary objective and other parts of protocol to remove the word compliance and changed to ease of use.	yes

## STUDY INFORMATION

### 1.0 Study Summary

#### 1.1 Synopsis

Study Title	Use of Liquid Stable Levothyroxine in Trisomy 21 Pediatric Patients
Study Design	Single-center, pilot, randomized, open-label crossover study
Primary Objective	Assessment of and tolerability ease of use of levothyroxine therapy based on CareCAT validation tool and medication administration log
Secondary Objective(s)	Compare biochemical effect of liquid stable LT4 versus tablet LT4 on TSH and FT4 in T21 hypothyroid patients
Research Intervention(s)/ Investigational Agent(s)	Tirosint®-SOL liquid stable levothyroxine
IND/IDE#	N/A
Study Population	Pediatric patients with Trisomy 21 and hypothyroidism
Sample Size	22
Study Duration for Individual Participants	Approximately 4 months
Study Specific Abbreviations/ Definitions	CH – congenital hypothyroidism CMH – Children’s Mercy Hospital FT4 – Free thyroxine GI – gastrointestinal LT4 – levothyroxine SOC – standard of care TSH – thyroid stimulating hormone T21 – Trisomy 21

### 2.0 Objectives

**2.1 Purpose, specific aims, or objectives:** Hypothyroidism is a common medical disorder in children with Trisomy 21 (T21). Treatment with oral tablet levothyroxine (LT4) is primarily used to treat this condition. However, children with T21 have developmental delay and other functional gastrointestinal (GI) issues that may negatively affect LT4 tolerability and absorption. For an age group unable to swallow tablets whole by mouth, tablets must be crushed and suspended in water, breast milk or formula for administration to treat children with hypothyroidism. For this age group, ease of administration may have a significant impact on compliance and ability to remain euthyroid. Until recently, there was no liquid preparation of LT4 in the United States for use in children.

Tirosint®-SOL (liquid stable LT4) is now FDA-approved for use in children. We propose that Tirosint®-SOL will be more favorably received due to ease of administration, improved tolerability, and palatability, therefore leading to improved adherence when compared to LT4 tablets. Our aims for this study are as follows:

- **Aim 1:** *Utilize medication tolerability questionnaire, CareCAT, to understand parental perceptions of liquid stable LT4*
- **Aim 2:** *Evaluate differences in ease of use of liquid stable LT4 compared to LT4 tablets*
- **Aim 3:** *Compare biochemical effect of liquid stable LT4 versus tablet LT4 on TSH and FT4 in T21 hypothyroid patients*

**2.2 Hypothesis:** We hypothesize that Tirosint®-SOL will be biochemically comparable to tablet LT4 as well as tolerated well and accepted by children with T21 and hypothyroidism ages 2 months to < 10 years. Caregivers will perceive Tirosint®-SOL as a preferred dosage form.

### 3.0 Background

**3.1** To date, there are no studies evaluating the response of liquid stable LT4 in hypothyroid T21 children.

**3.2** Trisomy 21 (T21) is one of the most common chromosomal disorders among live born infants. Its prevalence varies from 1 in 700 to 1 in 1500 live births. T21 is associated with many medical problems as well as developmental delay. Thyroid dysfunction is the most common endocrine abnormality and occurs in 4-8% of T21 children. Hypothyroidism in T21 has a prevalence estimated to be 28-35 times higher than the general population. Not all the mechanisms of hypothyroidism in T21 are known. Autoimmune hypothyroidism is one common etiology as children with T21 have increased prevalence of autoimmunity. Other possible etiologies include: 1. Exaggerated response to TRH stimulation in response to delayed maturation of hypothalamic – pituitary – thyroid axis; 2. Peripheral resistance to thyroid hormones (T4 and T3); 3. Reduced dopamine inhibition of TSH from altered dopaminergic regulation; and 4. Reduced TSH bioactivity. Due to these complex interactions, the use of traditional oral LT4 can lead to persistent elevation of TSH in 20-50% of hypothyroid T21 patients. The use of adjunctive liothyronine (L-T3) has been used to help normalize TSH but at the expense of complicating medication therapy. Recently, a liquid stable formulation of LT4 has been FDA approved for children in the United States. This form has been approved, extensively studied, and utilized in Europe for many years. Tirosint®-SOL is packaged in mono-dose ampules in 12 different dosage strengths. Tirosint®-SOL may be administered either directly into the mouth or a spoon or diluted in a glass of water. This novel form of LT4 has advantages in pharmacokinetic profile compared to traditional tablet LT4 due to direct intestinal absorption without a dissolution phase.

Traditional LT4 exists as a sodium salt that requires optimal acidic environment for dissolution and is susceptible to drug interference with calcium and iron supplements, estrogen, and other medications. On average approximately three quarters of the tablet LT4 is effectively absorbed. In contrast, multiple studies have demonstrated liquid stable LT4 is less affected by concomitant medication and supplement administration, offers improved biochemical levels of TSH, FT4 and FT3, and improved treatment compliance.

## 4.0 Study Endpoints

- 4.1 Primary endpoint:** *Parent perception responses from CareCAT medication tolerability tool*
- 4.2 Secondary endpoint:** *TSH and FT4 drawn 8-weeks post intervention*
- 4.3 Tertiary endpoint:** *linear growth (height), weight gain, and head circumference growth*

## 5.0 Study Design

**5.1 Study Design:** This is a single-center, pilot, randomized, open-label, cross-over study to determine satisfaction of standard LT4 tablets compared to liquid stable LT4 (Tirosint® -SOL) therapy and biochemical comparability in 22 participants diagnosed with Trisomy 21 and congenital or acquired hypothyroidism already on levothyroxine (LT4). Participants will be randomized in a 1:1 ratio to treatment (Tirosint®-SOL) or control (conventional therapy with LT4 tablets) for 8 weeks, at which point they will then crossover to receive the treatment arm they were not initially randomized to receive.

Participants will continue their same daily dose of LT4 or Tirosint®-SOL within the randomly assigned treatment group. Dose adjustments are allowed as needed, based on laboratory results and clinical response. Once enrolled, participants will be treated for 16 weeks total. The study will involve up to 3 in-person visits and 2 safety phone calls. Enrollment visit may be done via approved CMH video conferencing platform.

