## **24.0 Statistical Analysis**

## **25.0 Data and Specimen Management**

## **26.0 Setting & Location**

**26.1** This study will be conducted at any of the CMH Endocrine Clinics or virtually through a CMH approved video conferencing platform. No community advisory boards will be involved in the research study. No study procedures will be conducted outside of the CMH organization. Participants will be given contact information for both the PI and lead Nurse Coordinator. If laboratory results reflect a need in dose change, the child's provider will be consulted for that decision. No other anticipated medical or psychological resources are anticipated.

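### Does allowing dose changes on TSH/FT4, which are also the secondary endpoint, call for a change to the Aim 3 comparison?

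*Protocol*

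**What the plan says.** Section 5.1 sets the default: "Participants will continue their same daily dose of LT4 or Tirosint®-SOL within the randomly assigned treatment group". The next sentence gives the exception: "Dose adjustments are allowed as needed, based on laboratory results and clinical response". Section 26.1 sends laboratory-driven changes ("If laboratory results reflect a need in dose change") to the child's own provider.

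Section 4.2 defines the secondary endpoint as "TSH and FT4 drawn 8-weeks post intervention". The Table of Events (Section 5.2) schedules these labs three times: baseline (a standard-of-care result up to 6 weeks old), Visit 3 (Day 56 ± 4) and Visit 5 (Day 112 ± 4). Study drug for period 2 is dispensed at Visit 3, the visit of the Day 56 draw.

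Section 2.2 hypothesises that the liquid "will be biochemically comparable to tablet LT4". Section 3.2 reports that traditional oral LT4 can lead to "persistent elevation of TSH in 20-50% of hypothyroid T21 patients", and that liquid LT4 in other studies "offers improved biochemical levels of TSH, FT4 and FT3".

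**The concern.** In a crossover each child is his or her own control, so anything that differs between periods besides the formulation enters the contrast. Here the period-1 outcome can itself change the period-2 dose. A child with high TSH on tablets may start the liquid on a higher dose, and the lower Day 112 TSH would then be credited to the liquid. A child with high TSH on liquid may move to tablets on a higher dose, which alters the contrast the other way.

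Raised results are likely, given the rate in Section 3.2. Sections 4.2 and Aim 3 speak of TSH and FT4 only, and the Table of Events has no row for dose. A reader could therefore call the formulations comparable, or different, without knowing whether the doses were equal. At stake is the biochemical comparison, which is secondary. The primary endpoint is CareCAT.

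**Working it through.** **Timing.** Two periods of 8 weeks give 16 × 7 = 112 days, matching Visit 5. A change made on the Day 56 result cannot alter the Day 56 value. It acts at or after crossover, on Day 112. Within a period no TSH/FT4 is scheduled before the endpoint draw, so earlier changes need the baseline result, an unscheduled lab or clinical response.

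**How many children.** Applying 20–50% to all 22 gives 22 × 0.20 = 4.4 to 22 × 0.50 = 11. That is an upper reading: the rate is for traditional oral LT4, about half the children are on liquid at Day 56, and not every raised value leads to a change.

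**Direction, in closed form.** Let d be the true liquid-minus-tablet difference in log TSH at equal dose. Suppose a fraction k of each child's Day 56 deviation from target is corrected in period 2, with the average child on target.
- Tablet then liquid: expected Day 112 minus Day 56 = d.
- Liquid then tablet: expected difference = -d - kd.
- Crossover estimate = half the difference = [d - (-d - kd)]/2 = d(1 + k/2).

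With d = 0 the estimate is unbiased for any k. With d = -0.40 it is -0.45 at k = 0.25 and -0.50 at k = 0.5. Changes made within a period, before its endpoint draw, pull the other way.

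**Size, by simulation.** All inputs below are assumptions, not protocol figures: log-TSH SD 0.7 between and 0.4 within child; slope 2–4 per unit log dose; upper limit set so that 20%, 35% or 50% exceed it on tablets; lower limit at the same ratio as 0.7 to 5; half or all out-of-range Day 56 results acted on; 11 children per sequence; 20,000 replicates.

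No-change SE = 0.4 × √(2/22) = 0.1206.

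| Dose step | SE, true 0 | Estimate, true -0.40 | Mean dose gap, true -0.40 |
|---|---|---|---|
| 15% | 0.126–0.151 | -0.41 to -0.46 | 0.7–1.5% |
| 50% | 0.146–0.241 | -0.44 to -0.57 | 1.9–4.3% |

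With true difference 0 the mean estimate is 0 in every setting. At the 15% step, effective n runs from 22 × (0.1206/0.126)² = 20 down to 22 × (0.1206/0.151)² = 14. The 50% row is there because the strengths in Section 6.1 are far apart: 50/38 = 1.32 to 25/13 = 1.92 for the solution, 75/50 = 1.5 and 50/25 = 2 for tablets.

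**Is there a cleaner estimate?** A comparison of the sequences at Day 56 alone escapes any change made on that result. Its SE is √[2 × (0.49 + 0.16)/11] = 0.344. Adjusted for baseline (correlation 0.49/0.65 = 0.754) it is √[2 × 0.65 × (1 - 0.754²)/11] = 0.226. The crossover's root mean squared error at the worst 15% setting is √(0.06² + 0.149²) = 0.16, which is smaller than both. At the worst 50% setting it is √(0.169² + 0.240²) = 0.29, still below 0.344 but above 0.226.

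**Would reporting dose help?** Dose is set after randomisation on the outcome itself, so adjusting for it would not restore the equal-dose contrast. Dose recorded only at Days 56 and 112 would not separate a change at crossover from one later in period 2. Expressed per kg, dose falls as a young child grows even when the daily dose is unchanged.

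**The case for a change.** The best case for acting is that it costs little. One line on dose and one sentence saying whether Aim 3 compares formulations at equal dose or under usual adjustment would tell the reader what the contrast means. With 22 children, losing the information of 2 to 8 matters. Similar TSH reached at different doses is also not the same finding as similar TSH at equal dose.

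Part of this stands. The estimand is worth naming, and a listing of daily dose in mcg/day with the date of each change would be useful beside the TSH and FT4 results. Both are reporting choices that analysts make in a SAP or report, and neither changes the estimate. The SAP is not at hand, and Sections 22.0 and 24.0 are bare headings in this copy, although the revision history says the statistical analysis was clarified in Revision 7. Their absence here cannot be held against the plan.

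The two sentences in Section 5.1 do not contradict each other. The first sets the starting rule and the second its exception. Restricting dose changes to protect a secondary endpoint would be a clinical decision, outside a statistical review.

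**Conclusion.** No change is called for. The Day 56 result can influence the period-2 dose, so some within-child contrasts will mix dose with formulation. Under the protocol's own hypothesis of comparability this costs precision only: at a 15% step, 22 children are worth about 14–20. If the formulations differ by 0.40 on log TSH, the estimate is exaggerated by about 0.01–0.06, at most half the no-change SE of 0.12.

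These sizes rest on assumed SDs, slope, step and action rates. At a 50% step the exaggeration reaches 0.04–0.17, so the effect is small only if dose steps are small. FT4 was not simulated. The conclusion does not depend on the exact size. Allowing dose changes in children on replacement therapy is a fair trade-off, the crossover remains the more accurate estimate at the smaller step, and stating or tabulating dose would neither remove the mixing nor reveal so small an average dose gap. What remains is a reporting clarification on a secondary endpoint of a pilot trial.

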## 5.2 Table of Events:

Procedures	Enrollment/BaseLine a Visit 1	Dosing Week 1 b Days 1-7	Study Visit 2 c Day 3 +/-1 day	Dosing Weeks 2-8 Days 8-56	Study Visit 3, Week 8 Day 56 +/- 4 days	Dosing Week 9 b Days 63-70	Study Visit 4 c Day 55 +/- 1 day	Dosing Weeks 10-16 Days 71-112	Study Visit 5 Day 112 +/- 4 days
Obtain permission/assent or consent	X								
Demographics	X								
Medical history	X								
Randomization	X								
Dispense study intervention	X				X				
Concomitant medication review	X		X		X		X		X
Head Circumference	X				X				X
Height	X				X				X
Weight	X				X				X
Labs (TSH & FT4)	X				X				X
Adverse event review			X		X		X		X
CareCAT Survey d		X				X			
Dosing Video e		X				X			
PQL Survey	X				X				
Medication Administration Log		X		X		X		X	

a: Head circumference, height, and weight and labs from enrollment/baseline visit will be collected from Standard of Care visit within the previous 6 weeks  
b: Day 1 and Day 9 will be the first day of study drug administration in each arm  
c: Study Visit 2 and Study Visit 4 will be phone calls  
d: CareCAT survey will be done once daily during Week 1 and Week 9  
e: Dosing videos to be done within first 5 days of dosing in each arm

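### Visit 5 is timed from study Day 1 and not from the first dose of the second formulation, and the table contradicts itself on when that dose falls

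*Protocol*

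**What the plan says.** Section 5.1 assigns each child to one formulation "for 8 weeks, at which point they will then crossover to receive the treatment arm they were not initially randomized to receive". It states no gap between periods, and adds: "Once enrolled, participants will be treated for 16 weeks total".

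In Section 5.2 the end of period 1 is "Study Visit 3, Week 8 Day 56 +/- 4 days" and the end of period 2 is "Study Visit 5 Day 112 +/- 4 days". TSH and FT4 are drawn at both visits. The row "Dispense study intervention" is marked at Visits 1 and 3 only.

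The same table says different things about when period 2 begins:

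- The last dosing column of period 1 is "Dosing Weeks 2-8 Days 8-56", but the next one, Dosing Week 9, is printed as Days 63 to 70. Days 57 to 62 belong to no dosing column.
- Footnote b reads: "Day 1 and Day 9 will be the first day of study drug administration in each arm".
- Visit 4, the phone call of period 2, is set at Day 55 +/- 1, before the nominal crossover visit.

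Section 4.2 defines the secondary endpoint as "TSH and FT4 drawn 8-weeks post intervention". Aim 3 in Section 2.1 compares the two formulations on these two measurements.

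**The concern.** In a crossover, each child's value on one product is set against the same child's value on the other, so time on product should be alike at the two draws. Here the draw on the first product is tied to that product's start, because Day 1 is both the first dose and the origin of the count. The draw on the second product is tied to Day 1 as well, although that product starts about 8 weeks later, on a day that the table does not fix.

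If the second product starts when it is dispensed at Visit 3, its start moves with the Visit 3 window while Visit 5 does not. A late Visit 3 then lengthens period 1 and shortens period 2 by the same number of days. If it starts on the printed Day 63, period 2 is short for nearly everyone. In both cases the draw at Visit 5 may not match the 8 weeks in Section 4.2.

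**Working it through.** **Inputs (Section 5.2).** Visit 3 falls on Days 52 to 60 and Visit 5 on Days 108 to 116. I read the Section 4.2 endpoint as 8 weeks on each product, since the draws are at the end of each period.

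**The plan's own figure.** 2 periods x 8 weeks x 7 days = 112 days. This reproduces Day 112 and agrees with the 16 weeks in Section 5.1.

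**Consistency of the period 2 labels.** 8 x 7 = 56, so counting weeks from Day 1 makes Week 9 Days 57 to 63, not 63 to 70. The printed columns for Weeks 9 to 16 (Days 63 to 70 and 71 to 112) cover 8 + 42 = 50 days, although eight weeks are 56.

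**Exposure at the draw, by start day**

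| Start of product | Shortest | Nominal | Longest |
|---|---|---|---|
| Period 1, Day 1 | 52 | 56 | 60 |
| Period 2, at Visit 3 | 108 - 60 = 48 | 112 - 56 = 56 | 116 - 52 = 64 |
| Period 2, Day 63 | 108 - 63 = 45 | 112 - 63 = 49 | 116 - 63 = 53 |

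In the Visit 3 row, these are dosing days if the first dose is the day after Visit 3. A same-day first dose adds one (49 to 65). In the Day 63 row, counting both end days gives 46 to 54. A Day 9 start would give 100 to 108 dosing days, which cannot be intended.

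**How often, if period 2 starts at Visit 3.** Assume that each visit day is independent and uniform over its nine allowed days, which gives 9 x 9 = 81 pairs. Period 2 lies outside 52 to 60 days when the two deviations differ by 5 or more: 2 x (4 + 3 + 2 + 1) = 20 pairs. 20/81 = 24.7%, or about 5 of 22 children. The extreme of 48 days is 1 pair in 81 (1.2%).

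**Spread of the within-child difference in days on product.** The variance of one visit day is (81 - 1)/12 = 6.67, so the SD is 2.58.

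- As written, period 2 minus period 1 = V5 - 2 x V3 (V3 and V5 being the visit days). SD = sqrt(1 + 4) x 2.58 = 5.8 days, range -12 to +12, mean 0.
- With Visit 5 timed from the second start: SD = sqrt(2) x 2.58 = 3.7 days, range -8 to +8, mean 0.

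**Growth.** Footnote a lets baseline height, weight and head circumference come from a visit up to 6 weeks (42 days) earlier. The period 1 growth interval can therefore run from 52 to 60 + 42 = 102 days. If that lag is uniform over 0 to 42 days, its variance is (43 x 43 - 1)/12 = 154. The variance of the difference between growth intervals is then 33.3 + 154 = 187 as written and 13.3 + 154 = 167 after the change, a fall of about 11%.

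**The case against.** **The start at Visit 3 is only one reading.** This stands. The dispensing row and Section 5.1 support it, but the printed Day 63 falls after the latest Visit 3 (Day 60) and is a feasible fixed start. In that case no windows stack. A reader might infer that 48 to 64 days is the one consequence of the table, or that stacking survives any correction of the day labels. The document supports neither. Stacking remains only if the reconciled start moves with Visit 3.

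**The growth endpoint looks most exposed, because gain scales with time.** A reader might infer this, but the document does not support it. Baseline age under footnote a dominates the interval, and no passage says that growth is compared between periods. Section 4.3 only lists growth as tertiary.

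**No bias is shown.** This stands for the Visit 3 reading: both periods are nominally 56 days, the windows are symmetric and sequence is randomized 1:1. The drop in SD from 5.8 to 3.7 days is a 60% fall in the variance of days on product. It should not be read as a gain in the precision of TSH or FT4.

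**The extremes are rare.** This also stands. 61 of 81 pairs (75%) already give 52 to 60 days.

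**The scheduling rule may be stated elsewhere.** Sections 10.0 and 24.0 appear only as headings in the text available, so this cannot be excluded. Text there would not remove the contradictions inside the table.

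**Windows around fixed days suit a 16-week total.** That is a fair preference, but it does not place the second draw on the clock that Section 4.2 uses.

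**Conclusion.** The point holds as a minor, inexpensive improvement. Visit 5 is not placed by time on the second product, and the start of period 2 is stated inconsistently, so the passages must be reconciled.

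On the Visit 3 reading, exposure to the second product is 48 to 64 days against 52 to 60 for the first. About a quarter of children fall outside 52 to 60, assuming independent uniform visit days; the protocol does not say how visits will actually spread. On the Day 63 reading, exposure is 45 to 53 days, so the second product would be measured about a week before 8 weeks.

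The effect on TSH and FT4 is expected to be small; the document gives nothing from which to calculate it. CareCAT is collected in Weeks 1 and 9 and does not depend on the Visit 5 window. The document does not support a claim of systematic bias, nor an argument resting on growth.

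**What to change.** 1. Reconcile the statements on the start of period 2 (dispensing at Visit 3, the day labels of Weeks 9 to 16, footnote b and the day of Visit 4). Which start day applies is for the sponsor to decide.
2. In the Table of Events, define Visit 5 as 56 +/- 4 days after the recorded first dose of the second formulation, with Day 112 as a nominal label only.
3. Record the date of first dose in each period.

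TSH and FT4 are then drawn after 52 to 60 days on each product, whichever start day is confirmed.

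The cost is a line in the table and two recorded dates. With a start at Visit 3, Visit 5 can fall on about Days 104 (52 + 52) to 120 (60 + 60) instead of 108 to 116, which still fits the approximate 4 months of participation. A few families may need a few more days of supply. If the confirmed start were Day 63, the nominal Visit 5 would be Day 63 + 56 = 119, and the Day 112 label and the 16-week total would have to be brought into line as well.

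### Four second-period day labels in the Table of Events contradict the 8-week crossover and 16-week total in Section 5.1 (minor)

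*Protocol*

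**What the plan says.** Protocol Section 5.1 randomizes participants to one formulation "for 8 weeks, at which point they will then crossover to receive the treatment arm they were not initially randomized to receive", and states that "participants will be treated for 16 weeks total".

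The Table of Events in Section 5.2 labels Week 1 as Days 1 to 7 and Weeks 2 to 8 as Days 8 to 56. It sets "Study Visit 3, Week 8 Day 56 +/- 4 days", where the second formulation is dispensed, and puts Visit 5 at Day 112. For the second period it labels Week 9 as Days 63 to 70 and the rest as "Dosing Weeks 10-16 Days 71-112". Visit 4 is dated Day 55, plus or minus one day.

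Four footnotes bear on this. Footnote b fixes the start of each period: "Day 1 and Day 9 will be the first day of study drug administration in each arm". By footnote c, the second and fourth visits are made by telephone. For the primary endpoint instrument, footnote d says "CareCAT survey will be done once daily during Week 1 and Week 9". The video has its own rule in footnote e: "Dosing videos to be done within first 5 days of dosing in each arm".

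**The concern.** Staff book calls, surveys and videos from this table, so its day labels are operational. In the first period the safety call comes on about the third dosing day and reviews adverse events and concomitant medication soon after treatment starts. Visit 4 is its counterpart after the switch. Dated Day 55, it nominally comes before the second formulation is in the family's hands, and it sits one day before Visit 3, which carries the same two reviews. The only adverse event review then left after the switch is Visit 5.

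The Week 9 column also holds the second-period CareCAT surveys, which supply the primary endpoint (Section 4.1), and the dosing video. The start of that week should be stated in one way only.

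**Working it through.** **Inputs.** Section 5.1: 8 weeks, then crossover; 16 weeks in total. Section 5.2: the day labels above; Visit 2 on Day 3 ± 1; Visit 3 on Day 56 ± 4; Visit 4 on Day 55 ± 1; Visit 5 on Day 112 ± 4.

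**Rule.** Week k covers Days 7(k − 1) + 1 to 7k. The length of a column is last day − first day + 1.

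**The plan's own anchors reproduce.** 8 × 7 = 56 (Visit 3) and 16 × 7 = 112 (Visit 5).

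| Column | Expected days | Stated days | Stated length |
|---|---|---|---|
| Week 1 | 1–7 | 1–7 | 7 |
| Weeks 2–8 | 8–56 | 8–56 | 49 |
| Week 9 | 57–63 | 63–70 | 8 |
| Weeks 10–16 | 64–112 | 71–112 | 42 |

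The first period sums to 7 + 49 = 56 days, as it should. The second sums to 8 + 42 = 50 instead of 56, so the four columns cover 106 of 112 days. Days 57 to 62 (62 − 57 + 1 = 6 days) are in no dosing column, although the week labels run on without a break.

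**Footnote b.** Day 9 lies in Week 2, inside the first period and 57 − 9 = 48 days before the expected start of the second.

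**Visit 4.** The window is Days 54 to 56. It falls 63 − 56 = 7 to 63 − 54 = 9 days before the table's own start of Week 9. The visible text does not say whether the second formulation starts on the day of Visit 3 or the day after, so both are assumptions here. With Visit 3 on Day 56:

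- Next-day start (Day 57): the whole window precedes the first dose.
- Same-day start (Day 56): the window reaches dosing day 1 at the latest.

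Visit 2, by comparison, covers dosing days 2 to 4. Visit 3 may move, so the word nominal is needed: an early Visit 3 (Day 53 with a same-day start, or Day 52 with a next-day start) would put the call on dosing days 2 to 4.

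**Does any start day satisfy every label?**

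- Start on Day 57: Days 63 to 70 are dosing days 63 − 57 + 1 = 7 to 70 − 57 + 1 = 14. A video made in that column cannot meet the five-day rule in footnote e.
- Start on Day 63: the second period up to Day 112 is 50 days. Either total treatment is 56 + 50 = 106 days, or the first formulation continues to Day 62 and the crossover is not at 8 weeks.
- Start on Day 9: the second formulation is not dispensed until Visit 3.

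None does.

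**The case against.** The strongest reply is that these are clerical slips that nobody would follow literally. Visit 4 is numbered after Visit 3 and stands after the Week 9 column. Footnote d ties CareCAT to Week 9 and footnote e ties the video to the start of each arm. Day 9 probably means Week 9. Day 55 may be a one-digit slip for Day 65, which would be the third day counted from the table's own Day 63. A misreading of that digit from the PDF cannot be excluded either.

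Most of this stands, and it limits the weight of the point. It does not make the labels right. Day 65 would fit only a Day 63 start, which conflicts with Section 5.1; counted from Day 57 it is dosing day 65 − 57 + 1 = 9. One misread digit also cannot account for the two column headings and footnote b.

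The safety reply also stands. Section 13.1 gives both products the same risks and notes that participants take levothyroxine anyway. Section 23.1 has parents asked at each visit about health changes since the previous contact, and Section 26.1 gives families contact details for the study team. An early event would be picked up late, at Visit 5, rather than missed.

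A reader might infer more: that TSH and FT4 timing is compromised, that the CareCAT comparison is biased, or that children go six days without treatment. The documents support none of these. The laboratory draws are at Visits 3 and 5, whose labels are correct. Footnotes d and e show when CareCAT and the video are meant to occur. The protocol text available describes no washout or treatment break, so the six days are a labelling gap.

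**Conclusion.** The contradiction is certain, because it follows from day counts within Sections 5.1 and 5.2. Four labels are wrong: Week 9, Weeks 10 to 16, Visit 4 and footnote b's Day 9. The likely intent can be recovered, but no single reading satisfies all the labels.

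The consequence is limited to the second early safety call. If held as dated around a nominal Visit 3, it misses the first days on the second formulation, and the next scheduled review is Visit 5, 112 − 55 = 57 days after the call. No effect on an endpoint is shown. Severity is minor.

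Two assumptions enter the corrected dates. Day 57 as first dose assumes a next-day start, which fits the Weeks 2 to 8 column ending on Day 56. Day 59 for Visit 4 is inferred from Visit 2 and is not stated in the protocol.

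**What to change.** - Relabel Week 9 as Days 57 to 63 and Weeks 10 to 16 as Days 64 to 112 (7 + 49 = 56 days).
- In footnote b, replace Day 9 with the first dose of the second formulation after Visit 3, nominally Day 57. This should agree with any switch-day instruction in Sections 10 and 11.
- Set Visit 4 to the third dosing day of the second formulation, plus or minus one day, nominally 57 + 2 = Day 59.
- Optional: because Visit 3 can move by four days either way, add one line saying that second-period CareCAT, the dosing video and the safety call are counted from the actual first dose of the second formulation.

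Visit 5 needs no re-timing. The cost is three column headings and one footnote, plus one line if the option is taken. No participants, visits or procedures are added.
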